### 6.5.1.2. Asymptomatic SARS-CoV-2 Infection

This is a secondary endpoint for Part A and exploratory endpoint for Part B. It is defined in participants with negative SARS-CoV-2 at baseline. Asymptomatic SARS-CoV-2 infection is identified by both the absence of symptoms and the presence of infection as detected by RT-PCR or serology tests. Specifically:

- Absent of COVID-19 symptoms within 14 days of positive virologic or serologic results
- AND at least one from below:
  - Positive serology test result based on bAb specific to SARS-CoV-2 nucleocapsid at scheduled visits, when blood samples for immunogenicity are collected, or
  - Positive RT-PCR test post-baseline (at scheduled or unscheduled/illness visits)

The date of documented asymptomatic SARS-CoV-2 infection is the earlier date of:

- Date of positive serology test result based on bAb specific to SARS-CoV-2 nucleocapsid, or
- Date of positive RT-PCR test post-baseline (at scheduled or unscheduled/illness visits), with absence of symptoms.

For Part A, the time to the documented asymptomatic SARS-CoV-2 infection will be calculated as:

Time to the asymptomatic SARS-CoV-2 infection = Date of asymptomatic SARS-CoV-2 infection – Date of first study dose + 1.

For Part B, the time to the documented asymptomatic SARS-CoV-2 infection will be calculated as:

Time to the asymptomatic SARS-CoV-2 infection = Date of asymptomatic SARS-CoV-2 infection – Date of BD + 1. Cases will be counted starting 14 days after the second dose and after the third dose, e.g., date of documented infection - Date of the second/third dose/BD  $\geq$  14.

Confidential

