### 3.2.2. Secondary COVID-19 and SARS-CoV-2 Infection Endpoints

The incidence of asymptomatic SARS-CoV-2 infection after mRNA-1273 vaccination in adult SOT recipients and healthy adult participants with negative SARS-CoV-2 at baseline will be evaluated by the following endpoints:

The incidence of asymptomatic SARS-CoV-2 infection among recipients of mRNA-1273 SARS-CoV-2 vaccine will be defined in participants with negative SARS-CoV-2 at baseline as:

- bAb levels against SARS-CoV-2 nucleocapsid protein negative (as measured by Roche Elecsys) at Day 1 that become positive (as measured by Roche Elecsys) counted starting 28 days after the second dose and 28 days after the third dose of vaccine, OR
- Positive reverse transcriptase polymerase chain reaction (RT-PCR) (central lab or local diagnostic tests) counted starting 14 days after the second and after the third dose of vaccine

The incidence of COVID-19 after vaccination with mRNA-1273 in SOT recipients and healthy participants will be evaluated by the following endpoints:

- First occurrence of COVID-19 starting 14 days after the second dose and after the third dose of vaccine, where COVID-19 is defined as symptomatic disease based on the following criteria:
  - The participant must have experienced at least TWO of the following symptoms: fever ( $\geq 38^{\circ}\text{C}/\geq 100.4^{\circ}\text{F}$ ), chills, myalgia, headache, sore throat, or new olfactory and taste disorder(s), OR
  - The participant must have experienced at least ONE of the following respiratory signs/symptoms: cough, shortness of breath or difficulty breathing, OR clinical or radiographical evidence of pneumonia, AND
  - The participant must have at least 1 nasopharyngeal (NP) swab, nasal swab, or saliva sample (or respiratory sample, if hospitalized) positive for SARS-CoV-2 by RT-PCR
- First occurrence of severe COVID-19 starting 14 days after the second dose and after the third dose of vaccine, where severe COVID-19 is defined as symptomatic COVID-19 AND any of the following:
  - Clinical signs indicative of severe systemic illness, respiratory rate  $\geq 30$  per minute, heart rate  $\geq 125$  beats per minute, oxygen saturation ( $\text{SpO}_2$ )  $\leq 93\%$  on room air at sea level, or partial pressure of oxygen ( $\text{PaO}_2$ )/fraction of inspired oxygen ( $\text{FIO}_2$ )  $< 300$  mm Hg, OR

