### **6.5.1. Endpoint Definitions/Derivations**

#### **6.5.1.1. SARS-CoV-2 Infection**

This is a combination of COVID-19 (defined in [Section 6.5.1.3](#)) and asymptomatic SARS-CoV-2 infection (defined in [Section 6.5.1.2](#)) for participants with negative SARS-CoV-2 status at baseline. The incidence of SARS-CoV-2 infection counted starting 14 days after the second dose, the third dose, and the BD of IP will be summarized by participant group. SARS-CoV-2 infection will be defined in participants with negative SARS-CoV-2 at baseline meeting the criteria below:

- bAb levels against SARS-CoV-2 nucleocapsid protein negative (as measured by Roche Elecsys) at Day 1 that becomes positive (as measured by Roche Elecsys) counted starting 28 days after the second dose (at Day 57); 28 days after the third dose (at Day 113); and 28 days after the BD (BD-Day 28) or later, OR
- Positive RT-PCR counted starting 14 days after the second dose, third dose, and BD of IP

Confidential

During the analysis, documented infection is counted starting 14 days after the second, third dose, and BD of IP, which requires positive serology test result based on bAb specific to SARS-CoV-2 nucleocapsid 28 days after the second, third dose, and BD, or a positive RT-PCR result starting 14 days after the second, third dose, and BD of IP. Derivation of this endpoint is summarized in [Table 1](#) below.

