**Table 1. Derivation for SARS-CoV-2 Infection**

Baseline SARS-CoV-2 Status	Post-baseline assessments		Endpoint: SARS-CoV-2 infection
	RT-PCR test post-baseline	bAb levels against SARS-CoV-2 Nucleocapsid	
Negative at Baseline of each part	Positive (either at scheduled NP swab test, or at symptom-prompt NP swab test 14 days after the second/third dose)		Case
Negative at Baseline of each part		Positive (28 days after the second, third dose, and BD or later) as measured by Roche Elecsys	Case

The date of documented infection will be the earlier of:

- Date of positive post-baseline RT-PCR result, or
- Date of positive post-baseline serology test result based on bAb specific to SARS-CoV-2 nucleocapsid

For Part A, the time to the first documented SARS-CoV-2 infection will be calculated as:

Time to the first SARS-CoV-2 infection = Date of the first infection – Date of first study dose + 1.

For Part B, the time to the first documented SARS-CoV-2 infection will be calculated as:

Time to the first SARS-CoV-2 infection = Date of the first infection – Date of BD + 1.

Cases will be counted starting 14 days after the second, third dose, and BD, e.g., date of documented infection - Date of the second/third dose/BD  $\geq$  14.

Confidential

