### 6.5.1.3.COVID-19

The incidence of the first occurrence of COVID-19 starting 14 days after the second, third dose, and BD of IP will be presented. COVID-19 is defined as symptomatic disease based on the criteria specified in [Section 3.2.2](#). Cases are defined as participants meeting clinical criteria based on both symptoms for COVID-19 and positive RT-PCR test results.

Surveillance for COVID-19 symptoms will be conducted every two weeks by either telephone calls or eDiary prompts (alternating). Subjects reporting COVID-19 symptoms, as defined in Section 7.3.2 of Protocol Amendment 4, will be arranged an illness visit to collect an NP swab.

For this endpoint, a COVID-19 case will be identified as a positive post-baseline RT-PCR test result, together with eligible symptoms as described below in [Table 2](#).

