### 6.5.2. Analysis of Infection Rates

For Part A and Part B, the number and percentage of subjects experiencing each of the infection events below will be summarized by participant group for the mITT Set:

- SARS-CoV-2 infection
- Asymptomatic SARS-CoV-2
- COVID-19
- Severe COVID-19
- Secondary case definition of COVID-19

For each of these summaries, the incidence rate (i.e. the infection rate) will be provided by participant group, calculated as the number of cases divided by the total person-time. The 95% CI of the incidence rate will be calculated using the exact method (Poisson distribution) and adjusted by person-time.

Person-time is defined as the total time from first dose of each part of the study (Part A or Part B) to the earliest of the following dates: date of event, dose date in next part, last date of study participation, censoring time, or efficacy data cutoff date.

For participants who are a case for symptomatic COVID-19, symptoms reported by these participants will be summarized.

For SARS-CoV-2 infection, asymptomatic SARS-CoV-2 infection, COVID-19, and severe COVID-19, the timeframe for the counting cases will begin at 14 days after the last planned dose and will differ by study arm:

- 2-dose unvaccinated without booster: from day 43 up to and including day 394,
- 3-dose unvaccinated without booster: from day 99 up to and including day 450,
- 3-dose previously vaccinated with Moderna COVID-19 vaccine without booster: from day 15 up to and including day 365.
- 2-dose unvaccinated with booster: from BD-Day 1 + 14 up to and including BD-Day 181.

Confidential

- 3-dose unvaccinated with booster: from BD-Day 1 + 14 up to and including BD-Day 181)
- 3-dose previously vaccinated with Moderna COVID-19 vaccine with booster: from BD-Day 1+ 14 up to and including BD-Day 181 .
- 3-dose previously vaccinated with mRNA or non-mRNA COVID-19 vaccine with booster: from BD-Day 1 + 14 up to and including BD-Day 181.

In addition, the COVID-19 and SARS-CoV-2 infection endpoints may be also analyzed by specimen types (i.e. NP swab, nasal swab, or saliva samples), calendar months, time periods, and all types of the diagnostic test (i.e., both RT-PCR results and other COVID-19 test results). The number and percentage of subjects experiencing COVID-19 may be summarized by specific variant groups. Listings of serum nAb and bAb levels against SARS-CoV-2, solicited ARs and unsolicited AEs will be provided for subjects infected by SARS-CoV-2.

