## **7. Changes from Planned Analyses in Protocol**

Not applicable.

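### The asymptomatic-infection rule checks symptoms only 14 days back from a positive scheduled nucleocapsid draw, although follow-up draws are 151 to 185 days apart, so some serology-only infections are labelled by visit timing

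*SAP*

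**What the plan says.** SAP 6.5.1.2 asks for both absence of symptoms and evidence of infection. It makes the first part specific as "Absent of COVID-19 symptoms within 14 days of positive virologic or serologic results". The second part is met by a positive RT-PCR or by "Positive serology test result based on bAb specific to SARS-CoV-2 nucleocapsid at scheduled visits, when blood samples for immunogenicity are collected". The event is dated at the positive result. No rule looks back to the last negative draw.

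The neighbouring definitions are:

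- **COVID-19 (SAP 6.5.1.3):** "Cases are defined as participants meeting clinical criteria based on both symptoms for COVID-19 and positive RT-PCR test results". The symptom date and the RT-PCR date must lie within 14 days of each other.
- **Secondary case definition (SAP 6.5.1.5):** one listed symptom plus a positive RT-PCR, with no limit on the time between them.
- **SARS-CoV-2 infection (SAP 6.5.1.1):** "This is a combination of COVID-19" and asymptomatic infection. Table 1, however, counts a case on RT-PCR alone or on nucleocapsid serology alone, whatever the symptoms; its serology row reads "28 days after the second, third dose, and BD or later) as measured by Roche Elecsys".

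The asymptomatic endpoint in protocol Section 2 (Table 1) has no symptom criterion. Nor does SAP 3.2.2, whose RT-PCR limb is limited only by timing ("central lab or local diagnostic tests) counted starting 14 days after the second and after the third dose of vaccine"). SAP Section 7, on changes from the protocol's planned analyses, says "Not applicable".

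**The concern.** A positive swab is close in time to the illness, so a 14-day symptom window around it is sensible. A seroconversion at a scheduled visit is different: it says only that infection happened after the last negative draw. Searching 14 days of a five- or six-month interval for symptoms does not establish that the infection was asymptomatic.

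Both COVID-19 definitions require RT-PCR, so a serology-only illness cannot be reclassified there. Protocol 3.1 provides for nucleocapsid samples at illness and convalescent visits, but SAP 6.5.1.2 uses scheduled draws only. Scheduled swabs stop at Day 57 (2 doses), Day 113 (3 doses) or Day 29 (Group A3), and Part B has only the pre-dose swab on BD-D1 (protocol 3.2). After that, RT-PCR evidence depends on prompted swabs, and serology is the only scheduled test.

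At stake is the meaning of the asymptomatic count, a secondary endpoint in Part A and an exploratory one in Part B.

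**Working it through.** The documents give no figure for this endpoint, so there is none to reproduce. The check is one of intervals and of how the definitions fit together.

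**Draw days** (protocol 3.1 and 3.1.1.2):

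- Groups A1 and A5: 57, 209, 394. Gaps 209 − 57 = 152 and 394 − 209 = 185.
- Group A2: 113, 265, 450. Gaps 265 − 113 = 152 and 450 − 265 = 185.
- Group A3: 29, 180, 365. Gaps 180 − 29 = 151 and 365 − 180 = 185.
- Part B: BD-D29, BD-D181. Gap 181 − 29 = 152.

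**Share of a follow-up interval that the check covers** (14 / gap):

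- 14/151 = 9.3%, leaving 151 − 14 = 137 days unchecked.
- 14/152 = 9.2%, leaving 138 days.
- 14/185 = 7.6%, leaving 171 days.

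With the visit allowances in the schedules of events, follow-up gaps run from 131 to 213 days, and the share from 14/213 = 6.6% to 14/131 = 10.7%.

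**Around dosing.** Draws are 28 days apart, so the check covers 14/28 = 50%. For the draw 28 days after the last dose, it reaches back to the start of the counting window: 57 − 14 = 43, matching SAP 6.5.2 ("2-dose unvaccinated without booster: from day 43 up to and including day 394"). For symptoms from that day on, the first post-dose interval has no gap. The difficulty therefore lies mainly in the later draws.

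**Two participants compared.** Both have recorded COVID-19 symptoms, no positive RT-PCR, a negative draw on Day 57 and a positive draw on Day 209.

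- Ill and recovered by Day 190: 209 − 190 = 19 days, outside the window. SAP 6.5.1.2 labels this participant asymptomatic.
- Ill on Day 200: 209 − 200 = 9 days, inside the window. This participant is not asymptomatic. Without RT-PCR the infection is not COVID-19 under 6.5.1.3 or 6.5.1.5, yet Table 1 counts it as a SARS-CoV-2 infection.

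Two consequences follow. The label depends on the visit calendar rather than on the illness. And Table 1 contains infections that belong to neither component named in 6.5.1.1, so total infection is not the combination described there.

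**The case against.** **Reported symptoms should lead to a swab.** Protocol 7.1.6 calls for an illness visit or consultation with a swab for CDC-defined symptoms, close contact or a suggestive medically attended event, with no minimum duration. A reader might infer a wide swab gap from protocol 7.3.1, which makes the illness visit depend on 48 hours' duration for symptoms other than fever, chills, cough or breathing difficulty. Section 7.1.6 does not support that inference; the two sections are inconsistent and should be reconciled. This objection largely stands. Those affected are participants whose swab was missed, late or negative, and nothing in the documents says how many there will be.

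**Confirmed cases are already kept out.** A reader might also infer that an RT-PCR-confirmed COVID-19 case with a later positive scheduled draw could be counted as asymptomatic. On its plain reading 6.5.1.2 prevents this: a case under 6.5.1.3 has symptoms within 14 days of a positive virologic result and so fails the first requirement. Only the secondary definition, which has no 14-day link, leaves room for doubt.

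**The protocol endpoint has no symptom test.** It would count the Day 190 participant too. That is true, but the SAP has chosen to add a criterion, and the criterion is incomplete for serology.

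**A long look-back will catch unrelated illness.** Headache, fatigue and congestion are common, and some of these participants will have had a negative swab. This stands. It is a reason to report an undetermined category beside the present count rather than to relabel participants as symptomatic.

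**Conclusion.** The concern holds as a minor point. Under the stated rule, a serology-only infection with recorded symptoms more than 14 days before the positive draw is labelled asymptomatic, and one with symptoms inside 14 days has no component to belong to. Both follow from the SAP text and the draw schedule.

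The 7.6% to 9.3% is a share of calendar time. Taking its complement as the share of participants mislabelled is tempting but unsupported: that would need uniform onset over the interval, and it would apply only to serology-only infections with recorded symptoms. The number of participants affected cannot be derived and could be zero. For scale only, and if all are in the mITT set, one relabelled participant moves the percentage by 1/20 = 5.0 points among 20 healthy adults and by 1/220 = 0.45 points among 220 transplant recipients.

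The endpoint is descriptive, with no formal hypothesis testing (protocol Section 8). Counts of total SARS-CoV-2 infection, COVID-19, severe COVID-19 and the secondary case definition are unaffected.

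**What to change.** 1. In SAP 6.5.1.2, keep the 14-day rule for RT-PCR detections.
2. For serology-only infections, check recorded COVID-19 symptoms back to the last negative nucleocapsid result from a scheduled draw, leaving out solicited reactions in the 7 days after an injection. Report those with symptoms as *symptom status undetermined*, split by negative swab or no swab, beside the count under the 14-day rule.
3. In SAP 6.5.1.1, state that SARS-CoV-2 infection is the sum of COVID-19, asymptomatic and remaining infections, the last including the undetermined ones.
4. In SAP Section 7, list the symptom criterion as an addition to the protocol endpoint, and align SAP 3.2.2 with it.
5. As a clarification only, state that a participant who already met the COVID-19 or secondary case definition in that part is not an asymptomatic case.

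The cost is SAP wording, one derivation and one table row. The look-back can use only symptoms recorded with a date. Information from safety calls goes into source documents (protocol 7.1.2) and may not be in the database. Part B calls are also sparse after BD-D22: the next is BD-D59, 59 − 22 = 37 days later, and they then come every 30 days. Some undetermined participants will have had unrelated symptoms. Showing both counts keeps these limits visible.

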From unvaccinated participants who receive 2 doses of vaccine (healthy adults [Group A5] and SOT recipients who decline to receive a third dose [Group A1]), blood samples will be collected at baseline (Day 1), Day 29 (28 days after dose 1), Day 57 (28 days after dose 2), Day 209 (6 months after dose 2), and Day 394 (12 months after dose 2).

From previously vaccinated SOT participants who receive 1 dose of mRNA-1273 (Group A3), blood samples will be collected at pre-dose 3 (Day 1), Day 29 (28 days after dose 3), Day 180 (6 months after dose 3), and Day 365 (12 months after dose 3).

These blood samples will be for the assessment of the following endpoints and analytes:

- Measurement of SARS-CoV-2-specific bAb and nAb responses

- Development of Ab directed against nonvaccine antigen (nucleocapsid protein), which will signify infection with SARS-CoV-2. Participants who tested positive for Ab against SARS-CoV-2 nucleocapsid protein at baseline can continue in the study.

From unvaccinated SOT participants (Group A1 and Group A2), blood samples for cell-mediated immunity (CMI) studies will also be collected at Day 1, Day 36, and Day 92 (SOT recipients receiving 3 doses [Group A2]) from a subset of up to 50 SOT participants, as well as, from 20 healthy controls (Group A5) (Day 1 and Day 36), and from a subset of at least 50 previously vaccinated SOT recipients (Group A3) at Day 1 and Day 8, for exploratory assessments to characterize T- and B-cell responses to vaccine.

The NP swab samples obtained at illness visits ([Section 7.3.1](#)) will be used as sources of SARS-CoV-2 for genetic sequencing.

SARS-CoV-2 bAb against the nonvaccine antigen (nucleocapsid protein) will also be collected at the Illness and Convalescent visits.

The number of cases of COVID-19 will be assessed throughout the study ([Section Error! Reference source not found.](#)). Once a participant is identified as a case of COVID-19, a convalescent visit will be scheduled approximately 28 days after the confirmed diagnosis for a clinical evaluation and immunologic assessment of SARS-CoV-2 infection.

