7.1.6. Assessments for SARS-CoV-2 Infection

Study participants will have NP samples collected for SARS-CoV-2 testing by RT-PCR at time points specified in the applicable SoE ([Section 10.1](#)). A study illness visit or a consultation will be arranged within 72 hours or as soon as possible to collect an NP or nasal swab sample (NP is preferred) to ascertain the presence of SARS-CoV-2 via RT-PCR if a participant experiences any of the following:

- Signs or symptoms of SARS-CoV-2 infection as defined by the CDC ([CDC 2020a](#))
- Close contact exposure to an individual confirmed to be infected with SARS-CoV-2
- MAAE suggesting a SARS-CoV-2 infection

If the participant had known close contact exposure to COVID-19 (eg, close contact exposure to someone with confirmed COVID-19), it will be captured in the COVID-19 exposure form.

If scheduled, the study illness visit may collect additional clinical information at the investigator's discretion, including but not limited to medical history, physical examination, blood sampling for

clinical laboratory testing, and nasal, saliva, and/or NP swab sampling for viral PCR (including multiplex PCR for respiratory viruses, including SARS-CoV-2) to evaluate the severity of the clinical case. Radiologic imaging studies may be conducted. During this visit, a blood sample will also be collected for immunologic assessment of SARS-CoV-2. All findings will be recorded in the eCRF.

If participants are confirmed to have SARS-CoV-2 infection, the investigator will notify the participant and the participant's primary care physician of the diagnosis. If the study participant does not have a primary care physician, the investigator will assist them in obtaining one. The participant will also be instructed on infection prevention measures consistent with local public health guidance.

Any confirmed symptomatic SARS-CoV-2 infection occurring in participants will be captured as an MAAE along with relevant concomitant medications and details about severity, seriousness, and outcome. Additionally, a convalescent visit will be scheduled approximately 28 days (+7 days) after diagnosis ([Section 7.3.2](#)). At this visit, an NP swab sampling for viral PCR and a blood sample will be collected for potential immunologic assessment of SARS-CoV-2 infection

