7.3.2. Follow-up/Convalescent Period After Diagnosis with COVID-19

Any confirmed COVID-19 occurring in a participant will be captured as an MAAE along with relevant concomitant medications and details about severity, seriousness, and outcome. A convalescent visit will be scheduled approximately 28 days (+7 days) after diagnosis. At this visit, an NP swab sampling for viral PCR and a blood sample will be collected for potential immunologic

assessment of SARS-CoV-2 infection. The investigator should determine if the criteria for severe COVID-19 have been met. If the participant is hospitalized, medically qualified study site personnel will try to obtain medical records and SARS-CoV-2 diagnostic results. If the participant is later discharged from the hospital during the 28 day period following diagnosis of COVID-19, the study site personnel will arrange for a resumption of the protocol schedule.

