**Table 2. Derivation for COVID-19**

	COVID-19
Post-baseline PCR results	Positive, AND
Systemic symptoms	at least TWO of the following systemic symptoms : Fever ( $\geq 38^{\circ}\text{C}/\geq 100.4^{\circ}\text{F}$ ), chills, myalgia, headache, sore throat, new olfactory and taste disorder(s); OR
Respiratory symptoms	at least ONE of the following respiratory signs/symptoms: cough, shortness of breath or difficulty breathing, OR clinical or radiographical evidence of pneumonia.

The date of documented COVID-19 (case) will be the later date of ([2 systemic symptoms reported, or respiratory symptom reported] and, [date of positive PCR test]). Specifically, the date of documented COVID-19 will be the later date of the following two dates (date of

Confidential

positive PCR test, and the date of eligible symptom(s)), and the two dates should be within 14 days of each other. Specifically:

- Date of positive PCR test,
- Date of eligible symptom(s), defined as earliest of
  - Respiratory symptom: earliest date of an eligible respiratory symptom is reported OR
  - Systemic symptoms: earliest date of the second eligible systemic symptom is reported

For Part A, the time to the first occurrence of COVID-19 will be calculated as:

Time to the first occurrence of COVID-19 = Date of documented COVID-19 – Date of first study dose + 1.

For Part B, the time to the first documented SARS-CoV-2 infection will be calculated as:

Time to the first occurrence of COVID-19 = Date of documented COVID-19 – Date of BD + 1.

Cases will be counted starting 14 days after the second dose, third dose, and BD, e.g., date of documented COVID-19 - Date of the second/third dose/BD  $\geq$  14.

[Table 3](#) includes the days when a RT-PCR test is scheduled for each of the 2-dose and the 3-dose regimens with/without booster. For the analysis of this endpoint, RT-PCR results at scheduled pre-dose visits will not be considered in the derivation of COVID-19 cases.

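### SAP 6.5.1.2 does not exclude participants who have already met the COVID-19 definition, so a confirmed case who is nucleocapsid-positive at a later scheduled draw can also be counted as an asymptomatic infection

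*SAP*

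**What the plan says.** SAP 6.5.1.2 sets two conditions for an asymptomatic infection in a participant who was negative at baseline. The first concerns symptoms: "Absent of COVID-19 symptoms within 14 days of positive virologic or serologic results". The second is at least one of two positive tests:

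- "Positive serology test result based on bAb specific to SARS-CoV-2 nucleocapsid at scheduled visits, when blood samples for immunogenicity are collected"
- "Positive RT-PCR test post-baseline (at scheduled or unscheduled/illness visits"

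The event date is the earlier of the positive serology date and the date of a positive RT-PCR without symptoms.

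For a COVID-19 case, the derivation around SAP Table 2 pairs a positive PCR with qualifying symptoms, "and the two dates should be within 14 days of each other". SAP 6.5.2 then states that "the number and percentage of subjects experiencing each of the infection events below will be summarized by participant group", with separate lines for the composite infection, asymptomatic infection, COVID-19, severe COVID-19 and the secondary case definition.

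The protocol ensures that cases are tested again. Section 7.3.2 says "A convalescent visit will be scheduled approximately 28 days (+7 days) after diagnosis", and Section 7.1.6 adds "At this visit, an NP swab sampling for viral PCR and a blood sample will be collected for potential immunologic assessment". Scheduled blood for nucleocapsid antibody continues through follow-up. In the 2-dose groups, for example, Protocol 3.1 lists "Day 57 (28 days after dose 2), Day 209 (6 months after dose 2), and Day 394 (12 months after dose 2".

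**The concern.** The symptom condition is attached to a test result, not to the participant's history. A person with confirmed COVID-19 who recovers and is nucleocapsid-positive at a draw months later has no symptoms within 14 days of that draw. That person therefore satisfies every stated condition for an asymptomatic infection, although the antibody reflects the symptomatic episode already counted.

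Asymptomatic infection is a secondary endpoint in Part A and exploratory in Part B. Its count and incidence rate would include people with confirmed symptomatic disease. Any split of infections into symptomatic and asymptomatic, such as the additional summary in Protocol 8.3.4, would overlap.

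**Working it through.** The plan states no figure for this endpoint, so the check compares the rules and then does date arithmetic.

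**1. Does any rule remove a prior case?**

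- SAP 6.5 excludes participants only on baseline or pre-booster status.
- SAP 6.5.2 sets no hierarchy among the five lines. Its person-time definition lists a censoring time but does not say what triggers it.
- The definition in Protocol Table 1 has no symptom criterion, so it supplies no exclusivity. SAP Section 1 gives the SAP precedence in any case.

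No rule does so.

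**2. How often does a scheduled draw fall outside the 14-day window?**

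Inputs are the counting windows in SAP 6.5.2 and the scheduled draws in Protocol 3.1 and 3.1.1.2. A case on day t can re-qualify if a later draw on day d has d − t > 14. The last such day is the final draw minus 15. The case day stands in for the symptom day: lingering symptoms shorten the gap and earlier onset lengthens it.

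| Group | Counting window (days) | Draws in window | Some later draw > 14 days away | Very next draw > 14 days away |
|---|---|---|---|---|
| A1/A5, unboosted | 43–394 (352) | 57, 209, 394 | 43–379: 337/352 = 96% | 307/352 = 87% |
| A2, unboosted | 99–450 (352) | 113, 265, 450 | 99–435: 337/352 = 96% | 307/352 = 87% |
| A3, unboosted | 15–365 (351) | 29, 180, 365 | 15–350: 336/351 = 96% | 306/351 = 87% |
| Part B | BD-D15–BD-D181 (167) | BD-D29, BD-D181 | 15–166: 152/167 = 91% | 137/167 = 82% |

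For the last column in A1/A5, days 58–194 (137 days, next draw 209) plus days 210–379 (170 days, next draw 394) give 307. These are shares of possible case days, not of cases.

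The first draw in each window is marginal: 57 − 43, 113 − 99, 29 − 15 and BD 29 − 15 all equal 14, so on nominal days it is not more than 14 days after any counted case date. It becomes a route only if symptoms began before the case date or the visit is late. The BD-D29 allowance of +14 days reaches BD-D43, and 43 − 15 = 28. BD-D181 is the main Part B route.

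**3. Which Part A participants have the later draws?**

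Boosted participants move to the Part B schedule at D120, D149 or D205 (Protocol Table 10). SAP Table 3 then gives them no Part A immunogenicity window after the Day 57 or Day 113 visit, and SAP 6.5.2 lists Part A counting windows only for arms without a booster. The Part A rows above therefore describe Group A1, which Protocol Table 2 does not move to Part B, and A2, A3 or A5 participants who take no booster.

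**4. The convalescent swab.**

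With onset on the diagnosis day the gap to the swab is 28 to 35 days; with onset 3 days earlier it is 31 to 38. Only onset a full 14 days after the positive PCR, with the swab on day 28, touches the limit (28 − 14 = 14). The timing would allow a second count, but this route also needs a PCR still positive at that visit, and the visit must count as scheduled or unscheduled.

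**5. Size.**

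Extra cases = f × C, where C is the number of COVID-19 cases. The ratio of reported to true asymptomatic cases is 1 + f × C/A, where A is the true asymptomatic number. Assumed for illustration: C = 20, A = 10, 200 participants.

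| f (assumed) | Extra | Asymptomatic line | Ratio | Extra, % of 200 | COVID-19 + asymptomatic lines | Composite |
|---|---|---|---|---|---|---|
| 0.25 | 5 | 15 | 1.5 | 2.5 | 35 | 30 |
| 0.5 | 10 | 20 | 2.0 | 5 | 40 | 30 |
| 0.9 | 18 | 28 | 2.8 | 9 | 48 | 30 |

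**The case against.** The strongest defence is that the two 14-day rules mirror each other. A COVID-19 case has symptoms within 14 days of a positive result, and an asymptomatic infection has none within 14 days of positive results, in the plural. Applied per participant across all results, no case could be asymptomatic. SAP 6.5.1.1 fits this, since it describes the composite as a combination of the two. The reading is possible but not stated, and the date rule works against it: attaching absence of symptoms to the RT-PCR date treats results one by one. Two programmers could follow the text and produce different counts.

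Four other points stand and limit the concern:

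- The convalescent visit is not named in SAP 6.5.1.2 and has its own row in the Part A schedules. SAP Table 1 counts PCR at scheduled or symptom-prompted swabs, and SAP Table 3 has no convalescent window. This route is secondary.
- Boosted participants have few later Part A draws. Anyone seropositive before the booster is excluded from the Part B mITT Set, so nothing carries over between parts.
- The infection lines need not add up even without the double count. A PCR-positive participant with one systemic symptom can be in the composite yet be neither a COVID-19 case nor asymptomatic.
- No hypothesis test or between-group comparison depends on this endpoint.

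**Conclusion.** The concern holds for the asymptomatic line. As written, SAP 6.5.1.2 allows a confirmed COVID-19 case to be counted again as an asymptomatic infection for the same episode, mainly through a scheduled nucleocapsid draw more than 14 days after symptoms. The inflation is f × C. Neither f nor an attack rate is in the documents, so the 5 to 18 extra cases and the ratios of 1.5 to 2.8 follow entirely from the assumed inputs and are not forecasts.

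Three stronger conclusions that a reader might draw are not supported:

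- **That total infections or COVID-19 counts are inflated.** The composite takes the earlier date and counts each participant once, and the COVID-19 derivation does not use these later symptom-free positives.
- **That nothing separates the two endpoints.** The 14-day rule does so for results close to the episode, and persisting symptoms also block a second count.
- **That every Part A case is exposed.** The exposure is mainly among unboosted participants.

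This is a counting error in a descriptive secondary endpoint and is worth correcting before database lock. It does not threaten the primary results.

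**What to change.** Add to SAP 6.5.1.2:

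- A participant who has met the COVID-19 or secondary case definition since the baseline of that part is not afterwards counted as an asymptomatic infection.
- Later positive serology or RT-PCR, including at the convalescent visit, is attributed to the infection already counted.
- Person-time for the asymptomatic line is censored at the date of that case. State this in SAP 6.5.2, where the censoring time is now undefined.

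The rule should run in one direction only. A general first-event rule would remove a genuine first COVID-19 occurrence in someone earlier found to be asymptomatically infected, and the protocol endpoint requires that occurrence to count in the COVID-19 lines.

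The cost is a short SAP addition and a programming filter. No new data are needed.
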